1.3.3 Schedule of assessments

Here are the schedules of assessments extracted from the protocol:

Study Schedule of Events

	Screening	Treatment Period										Follow up Period					
		1	2	3	4	5	5	9	13	17							
Weeks:																	
Visits:	V1	V2	V3	V4	V5	V6	V7	V8	V9	V10 (EOS)							
Days:	D-42 to D-21	D1	D2	D8	D15	D22	D29	D35	D65	D125							
Time windows:		+/- 15 min	+/- 1d	+/- 1d	+/- 1d	+/- 1d	+/- 1d	+/- 1d	+/- 7d	+/- 7d							
Subjects' disposition:	Outpatient	Inpatient															
Informed Consent, Demography, Medical & Surgical History, Prior Medications	X																
Safety Evaluations																	
Physical exam (incl. Body Height/Weight ^c) and Vital Signs, aural body temperature	X																X
12-lead Electrocardiograms (ECGs)	X																X
Concomitant Medication & Adverse Events	X	X	X	X	X	X	X	X	X	X	X	X	X	X	X	X	X
Safety Laboratory (Haematology, Biochemistry, Coagulation and Urinalysis)	X ⁱ																X
Pregnancy Test (WOCBP only) ^d	X																X
Urine Drug Assay & Alcohol test	X																
Smecta® (IID, morning, noon, evening)																	X ^b
Biological Samples																	
Blood Samples for Elemental Impurities and biobanking	X	X	X ^{a,e}	X ^b	X ^{a,e}	X	X	X	X								
Urine Collection (24-hour) for Elemental Impurities		X											X	X	X	X	
Faecal Samples for Microbiota	X ^g	X											X	X	X	X	X
Consistency of stools (Bristol scale) and frequency over 24h by subject ^h	X ⁱ	X											X	X	X	X	X

a Six samples on Day 1 (and Day 35): 2 hours after the first dose (ex.: Smecta® intake 7.00am, meal 7.30am, PK 9.00am), immediately before second dose (ex.: PK 11.30am, Smecta® intake just after at 11h.30, meal at 12.30), 3h post lunch dose (ex.: PK at 2.30pm), immediately before the third dose (ex.: PK at 6.30pm, Smecta® intake just after at 6.30pm and meal 7.30pm), 3h post evening dose (ex.: PK at 9.30pm) and 6h post evening dose (ex.: 00.30am), and one sample on Day 36 in the morning (ex.: PK at 7.00am, Smecta® intake just after at 7.00am and meal 7.30am)

b On pre-dose before dosing (morning, approximately 7am on Day 2, and on pre-dose of any of the dosing occasion on the other days)

c Body height only at screening.

SAP FINAL VERSION 1.0: 20 JUNE 2017

13/32

- d Pregnancy test: serum at screening and urine at baseline and EoS.
- e Time window for PK sampling: ± 15 min
- f To be performed 24h before the visit 3
- g 1 sample to be taken at screening visit at the CRU and 1 sample by the subject at home at Day-14 ± 1 day
- h Smecta® should be taken fasting and at least one hour before meal, except for breakfast at least 30 minutes before.
- i C-reactive protein to be analysed only at screening
- j Diary to be completed at screening retrospectively to cover the past 24h, and 24h before the Day-14 stool sample
- k To the extent possible, to collect the data over approximately 24h preceding the stool sample taken at the visit 24h (i.e. 1 day or more).

1.3.4 Planned sample size

The critical limit of 50µg/l of lead is chosen as being the most conservative value taken among various guidelines (risk of saturnism, observations under high lead exposure at work). The baseline blood lead concentration of 31,4µg/l is considered as being a mean blood lead concentration in a survey of 1949 adults (18-74 years old) living in France in 2006-2007 (Falq et al. 2011). This population is representative of the French population including different socio-demographic characteristics and environment risk factors such as: sex, age, smoking status, type of drinking water, leisure activities, age of housing, shellfish/crustacean consumption. Considering the inclusion and exclusion criteria defined for the study, the enrolled subjects should have BLL levels in the same range as reported in the survey. With a standard error to the mean of [0,56], the mean blood lead concentration of 31.4µg/l is at confidence 95% to be found within [29.82; 32.98] under similar conditions. The non-superiority Δ margin is a clinical choice calculated as the difference of: 50 – 31.4 = 18.6µg/l. A precision of 15% (coefficient of variation) (CV) of the bioanalytical assay has been considered in the determination of sample size. Based on the above considerations, a sample size of 29 subjects with baseline mean blood lead concentration no greater than 36 µg/l (<36 µg/l), is required to provide 81% power to reject the null hypothesis of a difference of means no greater than 18,6 µg/l ($\leq 18,6 \mu\text{g/l}$ considered as no difference of means). Considering potential drop-out, it is planned to enroll a total of 35 subjects to ensure that at least 29 subjects completed the study.

Subjects who prematurely discontinue after investigational medicinal product (IMP) administration will not be replaced.

2 SUBJECT POPULATIONS (ANALYSIS SETS)

2.1 Efficacy population

There is no efficacy assessment in this study.

2.2 Screened population

The screened population is all screened subjects in the study which have given an informed consent.

2.3 Included population

The included population is all included subjects in the study i.e. with a status “included” at the end of the baseline visit.

2.4 Safety population

The safety population is all subjects receiving at least one dose of study medication.

2.5 Intent-To-Treat (ITT) population

The ITT population is all subjects receiving at least one dose of study medication and having one pre-dose BLL and at least one post-dose BLL.

2.6 Per Protocol (PP) population

The Per Protocol population is all subjects in the ITT population who completed the last post-treatment follow-up visit without any major protocol deviation.

3 STATISTICAL METHODS

3.1 Statistical analysis strategy

The statistical analyses will be performed in accordance with ICH E9 guideline.

Statistical analyses described in this document will be performed by Biotrial Biometrics, Rennes, France.

3.1.1 Primary endpoint

The primary endpoint is to assess the absolute change in blood lead level (BLL) from baseline during treatment and post-treatment follow-up period.

3.1.2 Secondary endpoints

The secondary endpoints are to assess:

- the absolute change from baseline of concentrations of other selected Class I (i.e. arsenic, barium) and Class IIa elemental impurities (i.e.: cadmium, mercury, cobalt, vanadium, nickel) and aluminium in blood during treatment and post-treatment follow-up period.
- the absolute change from baseline of urinary concentrations of selected Class I and IIa elemental impurities (arsenic, barium, cadmium, mercury, cobalt, vanadium, nickel) and aluminium in urine at the end of Smecta® administration and during follow-up period.

3.1.3 Safety endpoints

The safety endpoints are:

- physical examination, vital signs, ECG,
- standard clinical laboratory tests,
- adverse events and treatment emergent adverse events (TEAE).

3.1.4 Exploratory endpoints

Different absolute changes from baseline will be described on the ITT population:

- Absolute changes from baseline of consistency of stools (as rated according to Bristol scale over 24h by the subject) and frequency at different study visits.
- The microbiota absolute changes analysis will be described in a specific and separate plan.

3.1.5 Multiplicity

There is no plan for multiple testing adjustments in this study.

3.1.6 Significance testing and estimation

The statistical analysis of safety and biological samples is only descriptive therefore no formal statistical significance testing will be performed.

3.2 Analysis methods

3.2.1 Efficacy

Not applicable.

3.2.2 Biological and clinical evaluations

3.2.2.1 Biological evaluations

Biological evaluations concern blood samples for elemental impurities, urine collection (24-hour) for elemental impurities.

The baseline for blood concentrations (lead and other elemental impurities) will be the average between the available screening and pre-dose (Day-1) values (as defined in [Appendix 1 \(5\)](#)).

For blood lead concentrations, absolute values and changes (as defined in [Appendix 1 \(6\)](#)) from BLL baseline will be summarized for all post-baseline time-points on the ITT and the PP population.

Additionally, for all follow-up time points, absolute changes from D36 (in the morning) will be calculated and summarized.

Corresponding listings will be provided on ITT population.

Plots of mean absolute changes over time (with 95% confidence interval) will be provided on ITT and PP population and individual corresponding plots on ITT population (one graph for full profile). For blood lead concentrations, same analyses by country will be presented.

For other elemental impurities blood concentrations, the analysis will also be described in the same way as for blood lead concentrations expect for plots of means and individual corresponding plots which will be provided only for arsenic and barium parameters.

The baseline for urine concentrations (lead and other elemental impurities) and Ae parameter will be defined as the last available (and reliable if applicable) assessment collected prior to receiving dose of Smecta® on Day 1.

For urine lead concentrations and other elemental impurities, the same approach for blood lead concentrations will be done expect that there will be no plots.

The cumulative amount of EI (Elemental Impurities) excreted in urine (the Ae parameter) will be calculated (as defined in [Appendix 1 \(7\)](#)) and summarized at each scheduled assessment with absolute changes from baseline and absolute changes from D36 (in the morning) and listed on ITT population. Plot of mean of this cumulative amount (with 95% confidence interval) will be provided on ITT population if the number of data above the limit of quantification is sufficient.

The volume of urine will be only listed on ITT population.

For summary statistics, the following will be presented: n, arithmetic mean with its 95% confidence interval, standard deviation (SD), median and the range (minimum, maximum).

Geometric mean with its 95% confidence interval, CV% and geometric CV% will also be presented.

To compute descriptive statistics, all <LOQ values are replaced by the numerical value (LOQ/2) throughout the dataset and all <LOD values are replaced by the numerical value (LOD/2) throughout the dataset.

In case of high blood level of lead at one or two of the baseline points, a sensitivity analysis may be performed for blood lead concentrations summary tables and figures, excluding the patients with such unexpected baseline results to avoid any confounding of the mean study results.

Modeling of lead levels in blood and urine may be performed if deemed necessary. If it is the case, the data analysis plan and the analysis will be reported in separate data analysis plan and report.

3.2.2.2 *Clinical evaluations*

Consistency of stools (Bristol scale) and frequency over 24h by subject will be assessed on ITT population.

The baseline will be defined as the last available (and reliable if applicable) assessment collected prior to receiving dose of Smecta® on Day 1.

Number of watery stools (type 6 or 7), non-watery stools (type 1 to 5 inclusive) and total number of stools will be calculated for each subject and visit and will be summarised by visit with absolute changes from baseline.

Mean scores for watery stools, non-watery stools and for all stools will be calculated for each subject and visit and will be summarised by visit with absolute change from baseline. Corresponding individual listings will be provided.

Figures of means for numbers of stools and mean scores per visit on all subjects will be presented for watery stools, non-watery stools and total number of stools.

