3.5 Rationale for the Study Design

Discussion of Design

The primary objective of the study is to investigate the Blood Lead Levels after the chronic oral administration of Smecta® in subjects suffering from chronic functional diarrhoea. In each subject, lead concentrations obtained at several occasions during and after dosing with Smecta® will be compared to each individual baseline data. Other elemental impurities levels will be assessed in blood comparatively to baseline. Moreover, 24h urine level of all these impurities will be collected and assessed by mean of validated analytical methods. Samples of biobanking will be collected for potential other elemental impurities assessments as well as the potential measurement of lead in plasma. Stools samples and the assessment of stool consistency and stool frequency will be also collected for microbiote assessment as ancillary study.

Considering the extensive distribution of lead in the body as well as its long term residence time, a post-treatment follow-up period of 3-months has been considered appropriate to detect any change in the elemental impurities within the frame of a chronic administration of Smecta®.

Dose Selection and Dosing Regimen

The dose of Diosmectite (i.e. 1 sachet (3g) TID) is the recommended dose for Smecta® in the indication of chronic diarrhoea in an adult population.

For the purpose of this study, and in order to potentially limit variability and increase the bioavailability of lead (higher at low pH) dosing of Smecta® will occur in condition of fast 30 minutes before breakfast, 1 hour before noon lunch and 1 hour before evening dinner.

Five (5) weeks can be considered as a repeated chronic administration as chronic diarrhoea is defined as usually lasting more than 4 weeks.

Population Selection and Sample Size

The targeted subject population to assess the primary endpoint are subjects with chronic functional diarrhoea, one of the indication of Smecta® with subjects treated daily for several weeks.

Indeed, lead absorption could be different in subjects with normal gastro-intestinal transit time from patients with various gastrointestinal disorders of organic origin. Moreover patient with acute diarrhoea require a treatment lasting usually for 3 to 7 days that is far from chronic condition

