6.2 Concomitant Therapy(ies)

Any other treatment should be taken at least 2 hours before or after the ingestion of Smecta®.

Drugs with a low therapeutic index are specifically excluded (e.g. digoxin, theophylline) if repeated daily intake is needed.

Antibiotics are forbidden during the study as they could interfere with microbiote evaluation.

Compounds containing Diosmectite or similar compounds or mine extracts, as well as other compounds containing elemental impurities such as antacids (e.g. Maalox) are excluded.

The list of excluded concomitant medications are listed in Attachment #4 Section 15.4.

During the study the Investigator should check if the subject has received any concomitant medication/therapy that is not permitted at study entry.

Subjects will provide information about all previous medication taken over the last month and investigational drug taken over the last 3 months, and medication taken during the study, and this information will be recorded on the appropriate eCRF.

Contraception

No specific contraception methods are required for the study participation. A pregnancy test will be performed on screening, baseline and end-of-study visit. Women are requested to be non pregnant at inclusion and not becoming pregnant during the treatment phase of the study.

Rescue Medication

Loperamide will be allowed as rescue medication should the chronic diarrhoea worsen during the study.

The recommended dose regimen will follow the SmPC of loperamide with a maximum daily dose not exceeding 12 mg.

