7.5 Exploratory Assessment(s)

Single faces samples will be collected at timepoint defined in the schedule of events (see Attachment #1_Section 15.1) and processed according to standardised techniques developed by an international consortium (International Human Microbiome Standards, IHMS, http://www.microbiome-standards.org/#). Detailed procedures for the collection, handling, storage, shipment and analyses of the samples will be described in the specific study manual. The stools samples taken after the end of the treatment period (e.g. from Day 65 to Day 125 visits) will be analysed only in case of a significant change of microbiota is observed during

the study treatment in order to assess the resilience (return to the baseline profile) of microbiota during the post study treatment period.

Consistency of stools (recorded and rated according to Bristol scale) (See attachment # 7_ Section15.7) and frequency will be assessed over 24h by the subject the day before Screening, Day-14, baseline (D-1), Day 8, Day 35, Day 65, Day 95 and Day 125 visits, collected in a diary and reported by the site in the eCRF.

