3.2.20 Covariates and analysis of subgroups

No covariates or analysis of subgroups are planned in this study.

Nevertheless, analyses by country (Netherlands and United Kingdom) will be presented for demographic and baseline characteristics and also for blood lead concentrations.

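### The stool summaries take no account of loperamide rescue, so change from baseline may be shifted in either direction by an unknown amount

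*SAP*

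**What the plan says.** Stool consistency and frequency after chronic Smecta form an exploratory (ancillary) objective in Protocol 2.3 and SAP 1.1.3. Under Protocol 7.5 the subject assesses them over 24 hours ahead of the following time points: "Screening, Day-14, baseline (D-1), Day 8, Day 35, Day 65, Day 95 and Day 125 visits, collected in a diary".

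The analysis is in SAP 3.2.2.2 (Clinical evaluations):

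- Population: "Consistency of stools (Bristol scale) and frequency over 24h by subject will be assessed on ITT population".
- Baseline: "The baseline will be defined as the last available (and reliable if applicable) assessment collected prior to receiving dose of Smecta® on Day 1".
- Counts: watery, non-watery and total, where the "total number of stools will be calculated for each subject and visit and will be summarised by visit with absolute changes from baseline".
- Scores: "Mean scores for watery stools, non-watery stools and for all stools will be calculated for each subject and visit", again summarised by visit with change from baseline.

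On rescue, Protocol 6.2 states: "Loperamide will be allowed as rescue medication should the chronic diarrhoea worsen during the study". The permission is not confined to the treatment period. Neither the exclusion criteria (Protocol 4.4) nor the excluded-medication list (Attachment 4) names loperamide, and no washout of antidiarrhoeals before Day -1 is stated.

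The SAP does not mention loperamide or rescue. On subsets, SAP 3.2.20 says: "No covariates or analysis of subgroups are planned in this study", with an exception only for summaries by country.

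**The concern.** Rescue use is triggered by the outcome being measured. A subject whose diarrhoea worsens may take loperamide, record few or firm stools in the diary window, and enter the visit mean as improved from baseline. Because each visit rests on roughly one day of diary, a single episode of rescue can determine that subject's value.

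The study has no control arm, so change from baseline is its only evidence on stools. Protocol 1.6 already expects symptoms to improve on Smecta, so readers are likely to take the means as the drug's effect. During the three months off treatment, loperamide in the diary windows at Day 65, 95 or 125 could make recurrence look smaller than it was. Conversely, a baseline diary completed on loperamide would make later improvement look smaller than it was.

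**Working it through.** **No plan figure to reproduce.** The 29 subjects and 81% power in Protocol 8.1.2 and SAP 1.3.4 concern blood lead. The stool endpoint has no sample-size basis.

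**Step 1. Does any SAP rule pick up rescue use in the stool data?**

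| Place | What it covers | Does it deal with rescue? |
|---|---|---|
| SAP 2.5, ITT population | At least one dose, one pre-dose and one post-dose blood lead value | No |
| SAP 3.2.2.2, stool baseline | Last available, reliable pre-dose assessment | No condition on antidiarrhoeal use |
| SAP 3.2.4.1, reliability | No technical problem, plausible value | No; a diary completed on loperamide passes |
| SAP 3.2.4.3, outliers | Implausible or outlying values | No |
| SAP 3.2.10, medications | Dated listings; frequency tables by preferred name | Recorded, but not linked to diary windows |
| SAP 3.2.11, prior diarrhoea medication | Tabulated as in 3.2.10 | Recorded, but not linked to the baseline diary |
| SAP Appendix 2, section 14.2.3 | One stool table and two figures, all on ITT | No supplementary version |

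SAP 3.2.10 defines a concomitant medication as one taken at any time after the Day 1 cut-off. Its frequency table therefore pools five weeks of treatment with about three months of follow-up. It cannot show how many subjects had loperamide in the diary window at Day 35 or Day 95.

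**Step 2. What shift could result?** Every input is an assumption, because the documents give neither a rescue rate nor an effect on stool count.

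- q_visit: share of subjects with loperamide in the diary window at a visit, 10 to 30%.
- q_base: the same share at baseline, 0 to 30%.
- L: stools per day fewer in users, 1 to 2.

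Shift in mean change from baseline = -(q_visit - q_base) × L.

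| q_base | q_visit | L = 1 | L = 2 |
|---|---|---|---|
| 0 | 0.10 | -0.1 | -0.2 |
| 0 | 0.30 | -0.3 | -0.6 |
| 0.30 | 0.30 | 0 | 0 |
| 0.30 | 0.10 | +0.2 | +0.4 |

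Negative means fewer stools than without loperamide (apparent benefit, or recurrence understated). Positive means improvement understated. With a larger assumed effect of 2 to 3 watery stools per day and no use at baseline, the range is 0.10 × 2 = 0.2 to 0.30 × 3 = 0.9 towards benefit.

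**Step 3. What the sign depends on.** It depends only on whether use at the visit exceeds use at baseline. The documents fix neither.

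**The case against.** The strongest reply is that little rests on these summaries. The endpoint is exploratory, no efficacy assessment is planned (Protocol 7.2, SAP 1.3.2.1), and no significance test on stools is specified. In a single-arm study, change from baseline cannot be attributed to Smecta with or without rescue. That stands, and it is why the point is minor.

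Second, rescue use is not invisible. Concomitant medication and adverse events are collected at every visit, including Day 65, 95 and 125 (Attachment 1). Loperamide would appear in the listings, and worsening of a pre-existing condition falls within the adverse event definition in Protocol 7.1.1.1. This also stands. What is missing is the link to the diary windows, which a reader could rebuild only by matching listings subject by subject.

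Three stronger readings are tempting, and the documents do not support them:

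- *Loperamide effects will be credited to Smecta and relapse will be hidden.* No rescue rate is given and the sign is open, so these outcomes are possible but not established.
- *The worst subjects are counted as responders.* The SAP defines no responder; it plans counts, mean scores and changes only.
- *The blood lead results are biased too.* Protocol 3.5 does say that "lead absorption could be different in subjects with normal gastro-intestinal transit time", but the sentence goes on to contrast them with patients who have organic gastrointestinal disease, and it serves to justify the choice of population. It does not show that a change of transit within a subject alters lead absorption, so nothing about the primary endpoint follows.

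**Conclusion.** The concern holds as a minor analysis point on an exploratory endpoint. Followed as written, SAP 3.2.2.2 mixes into the stool means any effect of a drug whose permitted use is triggered by worsening of the outcome itself, and no planned output shows at which visits this happened. The illustrative shift runs from -0.6 to +0.4 stools per day over the scenarios in the table, and to -0.9 under the larger assumed effect. It is zero if use is equal at baseline and at the visit, or if nobody uses loperamide in a diary window. These figures show scale only. They rest on assumed use and effect, and the true size and direction cannot be derived from the documents. The primary blood lead analysis is not affected by this point.

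**What to change.** In SAP 3.2.2.2:

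1. Use the recorded concomitant and prior medication dates to flag each stool diary window, baseline included, that overlaps loperamide use.
2. Report the number and percentage of flagged subjects at each visit beside the stool means.
3. Add one supplementary stool table showing flagged and unflagged records separately, or excluding flagged records, including subjects whose baseline is flagged.

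Keep observed values. Setting the change to zero in flagged windows would not be conservative. In an assumed example with 4 watery stools at baseline and 5 recorded after loperamide, the observed change of 5 - 4 = +1 would become 0, and recorded worsening would be erased.

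The cost is SAP wording, one derived flag and one extra table, with fewer records in the supplementary table. The flag may be imprecise: SAP Appendix 1 (9) works from start and end dates, with times only where available, so as-needed use entered as one span could flag windows in which no dose was taken. A footnote should say so. No new data collection is needed, and no change to the rescue rule is proposed.
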